- (4) Detailed documentation of the treatment sequence and mechanics. If there were incomplete data provided in the patient's file; the patient will then be excluded from the study.

11. Where and when potentially eligible participants will be identified (setting,

location and dates)

Recruiting patients from Ksar El Ainy – Cairo University, future university archive with their specific eligibility criteria once the paper work is approved

12. Whether participants formed a consecutive, random or convenience series:

Any Patient that passes the inclusion criteria in terms of file including patient full records, Mechanics used were well registered and the case was well finished based on that the patient will be enrolled.

No subdivisions will be done

C) Test method:**13. Index test & reference standard in sufficient detail to allow replication**

A- The Preanalytical Phase:

Patients should have finished their orthodontic department at Cairo University with full Records available

B- The Analytical Phase:

Experts will analyze the outcome resulting from decision support system regarding extraction or non-extraction and anchorage planning and whether it is comparable to those conventional decisions reached by the orthodontic clinicians during treatment planning

C- Postanalytical Phase: Calculation of the efficiency of the system

14. Rationale for choosing the reference standard

Conventional Decisions (Decisions made by Orthodontic Clinicians) concerning extraction or non-extraction and anchorage planning for well finished cases

15. Definition and rationale for test positivity cut-offs of the index test & reference standard:

The study will test the efficiency of the decision support system according to those by the Orthodontic Clinicians

16 a. Clinical information and reference standard results will be available to the performers of the index test

Index test performers will be blinded

16 b. Clinical information and index test results will be available to the assessors of the reference standard

The assessors will be blinded from the treatment mechanics and results

D) Statistical analysis

17. Methods for estimating or comparing measures of diagnostic accuracy

Co-relation analysis will be used to compare the outcomes of both methods (conventional & computerized)

Statistical analyses will be performed using SPSS (version 22.0; IBM Corp, Armonk, NY). More than 1 type of statistical analysis will be used to address the outcomes. Cohen's kappa coefficient will be used to measure the agreement between the 2 methods on the basis of choice of the same options without consideration of the value assigned to each option (qualitative data). If a value were assigned to the option, it would be given 1, and if it were not assigned, it would be given 0. Cohen's kappa coefficient is a more robust method than simple percentage agreement, and its value dictates the strength of agreement (<0.20, poor; 0.21-0.40, fair; 0.41-0.60, moderate; 0.61-0.80, good; and 0.81-1.00, very good).

The concordance correlation coefficient would be used to measure the agreement between the 2 methods on the basis of the values (%) assigned for each treatment option by the 2 methods (quantitative data).

A value of ≥ 1 , corresponds to perfect agreement; ≥ 0.8 , very good; ≥ 0.7 , good; ≥ 0.5 , moderate, ≥ 0.4 , fair; ≥ 0.3 , poor; and 0, no agreement.

The sum of absolute difference and the relative sum of absolute difference were used to measure the percent error between the 2 methods on the basis of the values assigned for each treatment option (quantitative data).

18. How indeterminate index test or reference standard results will be handled:

It is not applicable as the outcome will be based on decisions made by the program

19. How missing data on the index test and reference standard will be handled

Any Patient file with incomplete data will not be included from the beginning in the study

20. Sample size calculation and how it was determined

Sample size is being calculated and waiting for approval

IV. Ethics and dissemination**21. Research ethics approval**

This protocol will be reviewed by the Ethics Committee of Scientific Research –Faculty of Oral and Dental Medicine Cairo University

22. Protocol amendments

Any modification to the protocol which may have an impact on the conduct of the study, potential benefit of the patient or may affect patient safety will require a formal amendment to the protocol. Such amendment will be agreed upon by the Council of orthodontic Department.

23. Informed consent

Template will be reviewed by the Ethical committee and will be signed by the patients or their legal guardians

24. Confidentiality

All study-related information will be stored securely by the personnel conducting the study

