Other applications of skeletal anchorage, including distal movement of the entire dental arch to reduce incisor protrusion.

Skeletal anchorage, created by placing bone screws in either arch in the canine region, is the easiest and most effective way to close an extraction space by bringing posterior teeth forward. This is particularly advantageous when more forward movement is needed on one side than the other. In both minimum and maximum retraction, temporary anchorage devices (TADs) now make it much easier to handle what previously were very difficult situations.

7. Study objectives and hypotheses:

The aim of the study includes hypothesis

The program decisions will meet the decisions of the orthodontist in well finished cases in terms of extraction decision and anchorage planning

Objectives:

- To study the efficiency of the program decisions in terms of extraction/non-extraction
- Anchorage planning decisions

III. Methods:

A) Trial design

8. Data and records of previously treated patients at Cairo university and Future University will be collected from the archive before the index test is performed so that the decision support system will be constructed based on the given data

B) Participants:**9. Eligibility criteria:****Inclusion Criteria:**

- 1- Cases with well finished orthodontic treatment.
- 2- Cases with history of crowding more than 10 mm and requiring extraction.
- 3- Cases with no severe skeletal discrepancy.
- 4- Well documented cases with both pre-operative and post-operative records.
- 5- Patients with a full set of permanent teeth erupted

Exclusion Criteria:

- 1- Improperly finished orthodontic cases.
- 2- Cases with mild crowding managed by treatment options other than extraction.
- 3- Growing patients or showing any residual growth remaining in cephalometric analysis
- 4- Cases with severe skeletal discrepancy.
- 5- Poorly documented cases.
- 6- Patients not sticking to anchorage plan

10. On what basis potentially eligible participants will be identified:

Recruiting well finished cases having history of crowding from Kasr el Ainy with no severe skeletal discrepancy, cases should be well documented. The precise and complete documentation of the patients in terms of the presence of:

- (1) Preoperative and postoperative x-rays.
- (2) Good quality preoperative and postoperative photographs.
- (3) Preoperative and postoperative study models.

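### The decision support system is built from the archived cases, and nothing in the protocol separates those cases from the ones on which its agreement with clinicians is scored

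*Protocol*

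**What the plan says.** - **Item 8 (Trial design).** Records of previously treated patients at the two universities are "collected from the archive before the index test is performed so that the decision support system will be constructed based on the given data".
- **Items 9 to 12 (Participants).** There is one set of eligibility criteria and one series. It is drawn from the archives of the same two universities (item 11), and any eligible file is enrolled. Item 12 adds "No subdivisions will be done".
- **Item 9, inclusion criterion 2 and exclusion criterion 2.** The first admits "Cases with history of crowding more than 10 mm and requiring extraction"; the second removes "Cases with mild crowding managed by treatment options other than extraction".
- **Items 13 to 15 (Test method).** Experts examine the system's output and "whether it is comparable to those conventional decisions reached by the orthodontic clinicians during treatment planning". The reference standard is the clinicians' decision in well finished cases.
- **Item 16a.** "Index test performers will be blinded".
- **Item 17.** Cohen's kappa "will be used to measure the agreement between the 2 methods on the basis of choice of the same options", and a concordance correlation coefficient covers the assigned percentages. The kappa bands are descriptive labels; no success threshold is attached to them.
- **Item 20.** The sample size has not yet been fixed.
- **Section II, item 7 (hypothesis).** "The program decisions will meet the decisions of the orthodontist in well finished cases".
- **Section II, item 6 (Rationale).** The purpose is to help orthodontists decide from a patient's clinical data, which means patients the system has not seen.

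**The concern.** A system fitted to a set of recorded decisions reproduces those decisions better than it predicts decisions in other patients. Agreement computed on the building cases therefore mixes real predictive ability with fit to the particular sample. The study's question is how well the program matches clinicians, and its stated use is in new patients, so the bias would fall on the central result. The harm would be an inflated kappa or concordance and possibly a better strength label. No hypothesis test would change, because the protocol sets no success threshold.

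**Working it through.** **1. Text check.** The items that could separate the two uses of the cases are these:

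| Item | What it settles | Does it separate building from evaluation cases? |
|---|---|---|
| 8 | Archive records build the system | No |
| 9 to 11 | One set of criteria, same archives | No second set is defined |
| 12 | Sampling of the series; no subdivision | No split is provided |
| 13 to 15 | Program compared with clinicians' decisions | Does not say on which cases |
| 16a | Blinding of those who run the index test | Concerns people, not the building data |
| 17 | Kappa, concordance, absolute differences | No out-of-fold scoring |
| 26 | Programmer has access to the final dataset | Nothing withholds reference decisions earlier |

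No hold-out, cross-validation, lock of the system or external sample is described for this study.

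**2. Which decision is exposed.** The two eligibility criteria leave all or nearly all extraction cases, so the extraction reference hardly varies. Kappa is (observed − expected agreement) / (1 − expected agreement). Take 100 cases, all extraction in the reference, with the program saying extraction in 95:

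- One row per case: observed = 0.95; expected = 1 × 0.95 + 0 × 0.05 = 0.95; kappa = 0/0.05 = 0. If the program says extraction in all 100, expected = 1 and kappa is undefined.
- One 1/0 row per option, pooled (item 17 codes options 1 or 0): observed = 190/200 = 0.95; expected = 0.5 × 0.5 + 0.5 × 0.5 = 0.50; kappa = 0.45/0.50 = 0.90.

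The protocol does not say which coding applies. Under either, a program that almost always answers extraction would agree as well in new cases of the same kind, so reuse has little to inflate. Anchorage still varies between patients and is where the bias would act.

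**3. Illustrative size for anchorage.** The protocol gives no figure to reproduce. Assumptions: three classes (one of the groupings in the literature review; another there has four); 5, 10 or 20 predictors, 4 of them informative; best achievable accuracy 80% with equal shares. Expected agreement is then 1/3, and the best kappa is (0.80 − 0.333)/(1 − 0.333) = 0.70. Gap = mean kappa on building cases − mean kappa on 3,000 new cases, over 400 simulated studies per setting.

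Linear discriminant, range over 5 to 20 predictors:

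| n | Gap, equal shares | Gap, shares 60/25/15 |
|---|---|---|
| 50 | 0.10 to 0.44 | 0.13 to 0.47 |
| 100 | 0.05 to 0.22 | 0.06 to 0.25 |
| 200 | 0.03 to 0.11 | 0.03 to 0.13 |
| 300 | 0.02 to 0.07 | 0.02 to 0.09 |

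In round terms this is 0.1 to 0.45 at n = 50 and 0.02 to 0.08 at n = 300. With this learner no kappa band was crossed at n = 156 or more.

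The learner matters. At n = 200 with 10 predictors and equal shares, kappa on building versus new cases was 0.72 v 0.67 (gap 0.05) for the linear discriminant and 0.78 v 0.57 (gap 0.21) for 5-nearest-neighbour. The second pair moves from the protocol's moderate band to its good band. Concordance was not simulated.

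**The case against.** **Overlap is not stated.** This stands. A reader might infer that the protocol plainly scores the system on its own building cases, and take the no-subdivision sentence in item 12 or the programmer's access in item 26 as proof. Neither is proof. Item 12 answers a question about sampling and may refer to subgroups; item 26 concerns the final dataset. What remains is that item 8 builds from the archive, only one series is defined, and no text supplies a second.

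**The program may be coded from textbook rules.** The methods never name a learner, and the background reviews anchorage determinants at length. A fixed rule set not derived from these cases would escape the bias. Item 8, however, says that the system is constructed from the collected data.

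**Blinding in item 16a protects the comparison.** It covers the people who run the test, not the data on which the program was built.

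**A site hold-out may be intended.** Items 10 and 13A name only one of the two universities. No hold-out is stated, and item 8 draws building records from both.

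**Splitting belongs in the analysis plan.** Fold numbers and code do. Which cases build the system and which test it is a design matter that item 8 touches directly. It has to be settled before construction, because a case already used for building cannot be made unseen.

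**The figures depend on the inputs chosen.** This stands. A separate set of runs with a multinomial logistic model and a weaker, moderate signal gave gaps of 0.07 (n = 200, 10 predictors: 0.55 v 0.48) to 0.68 (n = 50, 20 predictors: 0.97 v 0.29). The direction agrees; the size does not carry over.

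**Extraction kappa is zero.** A reader might conclude this from the eligibility criteria. It holds only when each case is one row and the reference is constant; the pooled coding gives 0.90 at 95% agreement.

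**Conclusion.** The concern holds in a conditional form. The protocol builds the system from the archive, defines a single series from the same archives, and scores the program against the recorded decisions without separating the two uses. If, as item 8 most naturally reads, the same cases serve both purposes and the system is fitted to their decisions, agreement is biased upward for new patients, mainly for anchorage. The size is unknown. Under the stated assumptions it runs from negligible (about 0.02 with a linear discriminant, few predictors and n = 300) to large (about 0.45 with 20 predictors and n = 50), with larger gaps generally expected from flexible learners. Confidence is medium, because both the overlap and the fitting are inferred. It should be fixed before the system is built.

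**What to change.** Amend item 8 in one of three ways:

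1. State that evaluation cases are disjoint from building cases, that their reference decisions are withheld from the programmer until the system is fixed, and that kappa and concordance are computed only on them.
2. If the archive is too small to split, use cross-validation with every building step inside the folds, and report only out-of-fold agreement with its confidence interval.
3. If the program is a fixed rule set not derived from these cases, say so.

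How to split is for the investigators. Item 12 should be worded to match.

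**Cost.** Protocol wording and a split or cross-validation code. No new data collection is needed if the archive is large enough to split or cross-validation is used; with the sample size unset, this cannot be confirmed. The price is fewer cases per step, a less precise estimate and a less favourable kappa. In the linear discriminant runs, the standard deviation of one study's out-of-fold kappa was 0.10 to 0.13 at n = 50 and about 0.05 at n = 200. A 70:30 hold-out gave 0.17 to 0.22 and 0.08 to 0.10.

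### Eligibility admits only cases that require extraction, so the study cannot test the extraction versus non-extraction decision named in its first objective

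*Protocol*

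**What the plan says.** Protocol item 7 (Study objectives and hypotheses) gives as the first objective "To study the efficiency of the program decisions in terms of extraction/non-extraction", with anchorage planning as the second. Item 14 sets the reference standard as "Conventional Decisions (Decisions made by Orthodontic Clinicians) concerning extraction or non-extraction and anchorage planning for well finished cases". Item 13 has experts compare the system's output with what the clinicians reached at treatment planning. The research question, intended use and clinical role in item 6 describe the same two-way decision.

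Item 9 (Eligibility criteria) then requires, as inclusion 2, "Cases with history of crowding more than 10 mm and requiring extraction". Exclusion 2 removes "Cases with mild crowding managed by treatment options other than extraction". Item 12 enrols "Any Patient that passes the inclusion criteria in terms of file including patient full records" and rules out subdivisions.

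For the analysis, item 17 plans Cohen's kappa on coded options: "If a value were assigned to the option, it would be given 1, and if it were not assigned, it would be given 0". It adds a concordance correlation coefficient and absolute-difference measures on percentage values. Item 20 reads "Sample size is being calculated and waiting for approval".

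**The concern.** Cases are selected on the very decision that the program is meant to be judged on. Inclusion 2 fixes the clinicians' answer at extraction for everyone who enters. Exclusion 2 on its own would still leave non-extraction cases with more than mild crowding, but inclusion 2 removes those as well.

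Whether a program can tell two groups apart cannot be learned from one group. A high agreement figure could then be reported as support for extraction/non-extraction decisions although no non-extraction decision had been tested. The design would also reward a program that makes no decision at all and simply answers extraction each time.

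There is a related consequence. Item 8 says the system is built from the collected archive records, so as written it would also be built without non-extraction cases.

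**Working it through.** The protocol gives no sample size, power or accuracy figure, so there is no stated number to reproduce. The check starts from the two-by-two table that the eligibility criteria imply.

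**Inputs.** From the protocol: the reference is extraction in every case (items 9, 12 and 14), and kappa is computed on 1/0 codes (item 17). Assumed for illustration: n = 100, the error counts, two example programs and the case mixes.

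**Specificity.** Specificity = TN / (TN + FP). Both counts come from reference non-extraction cases, of which there are none. The result is 0/0 at any n.

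**Kappa, one rating per case.** Let p be the share of cases that the program calls extraction.
- Observed agreement: Po = p.
- Expected agreement: Pe = 1 × p + 0 × (1 − p) = p.
- Kappa = (Po − Pe)/(1 − Pe) = 0 for every p below 1, and 0/0 at p = 1.

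**Kappa, 1/0 codes pooled over two complementary options.** Each rater codes one option 1 and the other 0 in every case, so each rater's marginal is 0.5.
- Pe = 0.5 × 0.5 + 0.5 × 0.5 = 0.5.
- Kappa = (p − 0.5)/0.5 = 2p − 1, which only restates raw agreement.

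| Program errors (n = 100) | Agreement p | Kappa, one rating | Kappa, pooled options |
|---|---|---|---|
| 0 | 100% | 0/0 | 1.00 |
| 1 | 99% | 0 | 0.98 |
| 5 | 95% | 0 | 0.90 |
| 10 | 90% | 0 | 0.80 |
| 20 | 80% | 0 | 0.60 |

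On item 17's own scale, where values below 0.20 are poor, 99% agreement would be labelled poor under the one-rating layout and very good under the pooled layout.

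**Two programs.** A always answers extraction. B has 95% sensitivity and 95% specificity. In a 70/30 mix, B calls extraction in 0.70 × 0.95 + 0.30 × 0.05 = 0.68 of cases. Then Pe = 0.70 × 0.68 + 0.30 × 0.32 = 0.572, and kappa = (0.95 − 0.572)/(1 − 0.572) = 0.378/0.428 = 0.88.

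| Measure | Eligible sample: A | Eligible sample: B | 70/30 mix: A | 70/30 mix: B |
|---|---|---|---|---|
| Agreement | 100% | 95% | 70% | 95% |
| Kappa, one rating | 0/0 | 0 | 0 | 0.88 |
| Kappa, pooled options | 1.00 | 0.90 | 0.40 | 0.90 |
| Specificity | not estimable | not estimable | 0% | 95% |

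The reversal does not depend on 70% in particular. At 50% and 90% extraction, one-rating kappa is 0 and 0 for A against 0.90 and 0.76 for B. Pooled kappa is 0.00 and 0.80 for A against 0.90 for B at both.

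**The case against.** Five points can be made on the other side.

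- **The reference may not be constant.** Item 16b blinds the reference assessors to treatment mechanics and results, which might suggest a fresh rating that could differ from the file. Items 13 and 14 nevertheless define the reference as the clinicians' treatment-planning decision, and 16b concerns blinding only. A case that required extraction but was treated without it would be incidental and would not form a usable comparison group.
- **Eligibility is loosely worded.** Item 10 mentions only a history of crowding, and exclusion 2 would be redundant if inclusion 2 already barred every non-extraction case. This may reveal a different intention, but item 10 is a summary and items 9 and 12 govern entry.
- **Kappa is not the only measure.** The concordance coefficient and difference measures on percentages may vary among extraction cases. That is so, but they still test no non-extraction case.
- **The hypothesis speaks of agreement, and the protocol never names specificity.** Agreement on extraction cases can indeed be estimated. The objective, however, is explicitly two-way, and agreement with a constant does not address it.
- **The kappa figures are hypothetical.** They depend on assumed inputs, and the pooled result needs complementary options. If both options of one case may carry a value, the kappa figures above do not apply. The zero denominator for specificity does not depend on any of this.

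**Conclusion.** The concern holds. As written, the eligibility criteria contradict the first objective: only its extraction side, in effect sensitivity, can be estimated, while specificity and discrimination cannot be estimated at any sample size. This rests on reading the reference as the clinicians' recorded treatment-planning decision, which is what items 13 and 14 say. The sizes shown for agreement and kappa are illustrations under stated assumptions. The anchorage objective is not damaged, because anchorage can vary among extraction cases. Since one of two stated objectives cannot be answered, and no later analysis can supply the missing cases, this should be settled before records are collected.

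**What to change.** Reconcile eligibility with the objective in one of two ways.

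1. **Make selection independent of the extraction decision.** Revise inclusion 2 and exclusion 2 so that well-finished non-extraction cases from the same archives also enter. Report sensitivity and specificity for extraction alongside kappa, and state the layout on which kappa is computed. The cost is revised wording, a wider archive search and more patients' records under the same ethics and consent handling. The system's construction under item 8 may be affected too. The protocol does not show how many fully documented, well-finished non-extraction cases exist. As the sample size is still open, it can be set for both groups.
2. **Narrow the claim.** Remove extraction/non-extraction from the objective and the hypothesis, carry the change through the research question, intended use and clinical role in item 6 and through items 13 and 14, and limit the conclusion to anchorage planning in extraction cases. The cost is wording only, at the price of a narrower claim.

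Which crowding criterion is clinically appropriate is for the investigators to decide.

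### Section 17 scores agreement option by option without fixing the patient as the unit of analysis, so a program giving everyone the same plan could be graded good or very good

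*Protocol*

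**What the plan says.** The hypothesis in section 7 concerns cases: "The program decisions will meet the decisions of the orthodontist in well finished cases". There are two objectives, the extraction decision and the anchorage plan.

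Section 17 then scores agreement by treatment option:

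- **Kappa.** "Cohen's kappa coefficient will be used to measure the agreement between the 2 methods on the basis of choice of the same options". The coding rule is "If a value were assigned to the option, it would be given 1, and if it were not assigned, it would be given 0".
- **Concordance correlation coefficient.** It measures agreement "on the basis of the values (%) assigned for each treatment option by the 2 methods".
- **Grading.** Each coefficient has verbal bands. The upper ones are "0.61-0.80, good; and 0.81-1.00, very good" for kappa and "≥ 0.8 , very good; ≥ 0.7 , good" for concordance.

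Section 17 does not say whether option scores are pooled over patients and options, computed within each patient, or computed for each option across patients. The methods do not list the options. Section 9 includes "Cases with history of crowding more than 10 mm and requiring extraction" and excludes mild crowding that was managed without extraction. Section 20 gives no sample size.

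**The concern.** The hypothesis asks whether the program reaches the clinician's decision for the individual case. Section 17 makes the option the scored item. These coincide only if the coefficient is computed across patients.

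If the option rows of all patients are pooled, each option has the same chance rate, 1/K, however common it is in practice. Shared zeros on unchosen options also count as agreement. In pooled percentages, the gap between a usually high option and a usually low one counts as concordance between the methods. A program that cannot tell patients apart could then receive one of the top two grades. Those grades are a main way in which the study will describe its result.

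**Working it through.** **Inputs.** The coding and the bands come from section 17. The protocol gives no expected kappa, option list, option shares or sample size, so there is no figure of its own to reproduce. Assumptions, shown as ranges: one option chosen per case; K = 2 or 3 options (the literature review describes a three-group anchorage classification); and a program that always outputs the commonest plan, which is the clinicians' choice in a share p of cases. The results do not depend on the number of patients.

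**1. Kappa pooled over patient-by-option cells.** Where the methods agree on a case, all K cells match; where they disagree, K − 2 match.

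- Observed agreement = 1 − 2(1 − p)/K.
- Each method has a share 1/K of ones, so chance agreement = 1 − 2(K − 1)/K².
- Kappa = 1 − (1 − p)K/(K − 1).

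| p | K = 2 | K = 3 |
|---|---|---|
| 0.80 | 0.60 | 0.70 |
| 0.85 | 0.70 | 0.775 |
| 0.90 | 0.80 | 0.85 |
| 0.95 | 0.90 | 0.925 |

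Lowest p for *good* (0.61) is 1 − 0.39(K − 1)/K: 0.805 with two options, 0.74 with three. Lowest p for *very good* (0.81) is 1 − 0.19(K − 1)/K: 0.905 and 0.873.

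**2. Kappa within each patient, then averaged.** An agreeing case scores 1 and a disagreeing case −1/(K − 1). The mean, p − (1 − p)/(K − 1), equals the expression in step 1.

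**3. Kappa across patients.** For a program with constant output, observed agreement is p and chance agreement is also p. Kappa = (p − p)/(1 − p) = 0 for every p below 1, and is undefined (0/0) at p = 1. This holds for the whole decision and for each option separately.

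**4. Concordance, two options.** The coefficient is twice the covariance, divided by the sum of the two variances plus the squared mean difference.

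- Both methods give about 90/10 (SD 8), unrelated across patients. Pooled covariance is 40² = 1600 and each variance is 1600 + 64 = 1664, so the coefficient is 1600/1664 = 0.96.
- The program as above; the reference is 100/0, with 90% of cases on one option. Reference variance is 2500 and covariance 40 × 40 = 1600, so the coefficient is 3200/(2500 + 1664) = 0.77.
- Per option across patients, both are 0.

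**5. Both objectives pooled.** Suppose the clinicians always choose extraction, as section 9 implies, and there are three anchorage classes whose commonest has share q. Five cells per patient contain two ones, so observed agreement is 1 − 2(1 − q)/5 and chance agreement is 0.4² + 0.6² = 0.52. Kappa = 1 − (1 − q)/1.2: 0.44 at q = 1/3, 0.62 (*good*) at q = 0.54 and 0.82 (*very good*) at q = 0.78. Kappa across patients for anchorage is 0 at each of these.

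**6. Extraction across patients under section 9.** If every clinician decision is extraction and the program says extraction in a share r of cases, observed and chance agreement both equal r. Kappa is 0, or undefined if r = 1.

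**The case against.** A reader might infer that the protocol computes its coefficients over options rather than patients. It does not say so. The wording about values for each treatment option also fits one coefficient per option across patients, and on that reading the same-plan program scores 0. Row layout is often left to an analysis plan, which is not available here. This stands, and limits the point to an unfixed unit of analysis. It does not remove it: the protocol itself fixes the option-wise coding and the bands, and two of the three plausible readings give the inflated value.

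Other stronger readings also fail:

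- *The grade reflects only which plan is common.* Pooled kappa equals (p − 1/K)/(1 − 1/K), so it depends on case-level agreement and K. Uniform chance correction is a recognised choice. The narrower criticism is that the result is not the Cohen's kappa across patients that its label suggests, and that it credits a constant program for the dominance of one plan.
- *Reported intervals will be too narrow.* Section 17 plans no interval or standard error.
- *Each patient has exactly one option.* The percentage scoring allows several options to carry values. The kappa formulas above would then not apply as given.
- *The grade is the only conclusion.* Section 17 also plans sums of absolute differences, and section 13 has experts compare the decisions.

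Nor is a high grade automatic. With two options and p = 0.80, pooled kappa is 0.60, below *good*, and no document figure gives the share of any anchorage class.

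**Conclusion.** The concern holds as a failure to fix the unit of analysis, combined with option-based scoring that permits a misleading grade. It does not hold as a claim that the planned coefficients are known to be wrong. With one option per case, pooled or within-patient kappa puts a same-plan program in the *good* band from a dominant-plan share of about 0.81 (two options) or 0.74 (three), and in the *very good* band from about 0.91 or 0.87. Pooled concordance in the two-option examples is 0.77 to 0.96. The corresponding values across patients are 0. The shares, the number of options and the single choice per case are assumptions. For extraction, the eligibility criteria as written make a dominant option close to certain. They also leave kappa across patients at 0 or undefined, so naming the unit does not by itself rescue that objective.

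**What to change.** In section 17:

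- State that the patient is the unit of analysis and that options are not pooled.
- Compute kappa separately for the extraction decision and the anchorage class, from one row per patient, with the program's category against the clinician's. Report the category totals of both methods beside each kappa.
- If several options can carry values in one patient, compute kappa for each option across patients instead.
- Compute any concordance coefficient separately for each option across patients.
- Base any interval that is reported on patients.

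Separately, reconcile section 9 with the extraction objective in section 7, since agreement beyond chance on that decision cannot be shown when all eligible cases required extraction.

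The section 17 change needs about a paragraph, with the same data and software. Its price is that the coefficients may look less favourable. Reconciling the eligibility criteria is a further change that the paragraph does not cover.
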